NOTE: We also plan to collect and store plasma, sera, and urine specimens from all screened / consenting aim 1 study participants for future analyses that we will perform by obtaining separate/additional grant funding; specifically storing specimens (-80°C) for future biomarker association and other relevant translational studies, and as a backup DNA source for quality control. We will also seek ancillary/supplemental funding to conduct 12- and 24-month follow-up of consenting Aim 1 patients for Aim 3 outcomes.

Aim 2 Study Procedures

Study Medication: Participants in the intervention arm will be given lisinopril at a starting dose of 5 mg/day at time of Aim 2 enrollment. Participants in the control arm will receive a matched placebo. Participants who are found to have symptomatic hypotension and/or new onset /persistent grade 3 (or higher) hyperkalemia after taking study medication (as evaluated at day 3 (safety phone call), week 1, month 1, or during an unscheduled visit will be removed from the study.

Participants who tolerate the initial study dose (5 mg/day or placebo) will be increased to 10 mg/day lisinopril (or matched placebo) at their one (1)-month study visit. All study participants having a dose change/escalation from 5 to 10 mg active medication (or matched placebo), will also (as was done following study enrollment) undergo safety monitoring in the form of a 3-day post dose escalation safety phone call, a 1-week post dose escalation study visit for blood draw/safety evaluation, and 1-month post dose escalation study visit for blood draw/safety evaluation. Those who do not tolerate an increase to the 10 mg/day dose will be returned to the 5 mg/day dose, while those who are able to tolerate an increase to the 10 mg/d dose will be closely monitored for

adverse events and re-assessed (see below) at their 3-month study visit for a possible dose escalation to 20 mg/d of lisinopril.

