Alternative medications: Patients who develop side effects to lisinopril (particularly refractory cough) will be transitioned to the equivalent dose of an angiotensin receptor blocker (ARB), losartan, at a dose of 25 or 50 mg/day (depending on the dose of lisinopril (or matched placebo) they were receiving at the time of their adverse event). Most patients that develop a refractory cough on lisinopril (which we believe will be few) if they need anti-hypertensive control will be switched from lisinopril to 50 mg/d of losartan. A few patients may develop a refractory cough very early on study medication (within first 1-2 months of enrollment), and such patients, if they still require antihypertensive medication control may be switched to 25 mg/d of losartan. Patients in need of anti-hypertensive treatment that developed a refractory cough while on study medication will all need to be unblinded due to the severity of this adverse event and most importantly so it can be listed on the patient's active list of medication side effects, so they will not be prescribed ACE inhibitors again in the future. Patients who do not tolerate either study medication (lisinopril or losartan) will be removed from the study and referred to care if needed (see **Figure 2** for details).

Figure 2. Flow diagram of study medication dosing. Endpoints are outlined in green. Symptomatic hypotension will be defined as a reading of lower than 90 mm Hg systolic

or 60 mm Hg diastolic with associated symptoms (i.e. feeling of lightheadedness, weakness) (**NOTE**: All low blood pressure readings will be confirmed, orthostatic blood pressure will be obtained (when clinically indicated/appropriate), and all readings will be put in context of the individual's normal BP readings). Patients removed from the study due to failure to tolerate either the primary (lisinopril) or alternative (losartan) study drug will be unblinded (outlined in **red**) so as to enable their physician to best treat any conditions. (**NOTE**: Hyperkalemia will be graded using established DAIDS Toxicity grading Scale (Version 2.1, July 2017); with grade 1 hyperkalemia = 5.6-5.99 mmol/L, grade 2 hyperkalemia = 6.0-6.49 mmol/L, grade 3 hyperkalemia = 6.5-6.99 mmol/L and grade 4 hyperkalemia (K+ values) being $\geq 7.0 \text{ mmol/L}$).

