NOTE: Females with reproductive potential will receive extensive education regarding the risks of ACEi therapy; namely the potential risk of congenital abnormalities during the first trimester (one study¹³¹) as well as the documented increased risk of fetal renal damage in the 2nd and 3rd trimesters.¹³² All reproductive-aged females will undergo preenrolment and q 3-monthly urine pregnancy testing and, if they test positive, they will be immediately unblinded and their study medication (if on active study medication; i.e. lisinopril) will be discontinued immediately and an appropriate substitution will be made if needed (i.e. anti-hypertensive).^{131,132} We will also educate all enrolled women having reproductive potential to immediately report to the study staff if they suspect being pregnant. If they do suspect being pregnant, they will immediately report to the research team, their ACEi will be discontinued, and they will undergo the necessary evaluations (i.e. urine pregnancy testing) with alternative anti-hypertensive medications being prescribed as needed among women confirmed as being pregnant. **Study medication and adherence:** The medication or placebo will be provided to each study participant at no cost to the participant. Study medications will be stored at the clinical site in a locked storage cabinet that will be accessible to the study pharmacist and site PI. The study pharmacist will ensure the medicine is stored properly and dispensed only when needed for study participants. The site investigators will assure the medicine is stored properly and dispensed only when need for study participants to by the clinical pharmacist designated at the clinical site. The following will be monitored and completed on a continuous basis to assure the medicine is within study guidelines, onsite pharmaceutical compliance, and manufacturer guidelines:

- 1. Delivery Log of Medication
- 2. Drug Accountability Record
- 3. Drug Safety and Handling Sheet

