The common side effects of lisinopril includes the following: cough, headache, dizziness, depressed mood, drowsiness, gastrointestinal symptoms such as nausea, upset stomach, vomiting or diarrhea, and skin symptoms such as mild itching or a rash. Any patients experiencing persistent/refractory cough that is deemed possibly related to their lisinopril therapy (as a refractory cough has been reported in as many as 6-8% of participants, with higher rates seen in person of African descent (up to 12% in some studies), will be switched to an equivalent dose of the ARB losartan, as described above. Patients switching from lisinopril to losartan will remain on study (Aim 2), as a switch from an ACEi to an ARB is an allowable study substitution. Common side effects of losartan include the following: cold or flu-like symptoms such as stuffy nose, sneezing, sore throat, fever; dry cough; muscle cramps; pain in legs or back; stomach pain or diarrhea; headache or dizziness; tired feeling or insomnia.

Refractory Cough: Cough occurs in 5-15% of patients. It is not dose- or brandrelated, is more frequent in women than men, and is more frequent in persons of African descent (blacks) than Caucasians (whites). It usually develops within 1 week to 6 months following ACEi initiation and typically resolves within 4 days of cessation. Study investigators need to be aware of a confounding congestive heart failure cough and remember that changing to another formulation sometimes helps. NOTE: Persons with a history of chronic h/o congestive heart failure are not eligible for aim 2. Cough is not a reason to discontinue treatment unless it persists (and or escalates in intensity/severity) and/or study participants feel that they cannot tolerate it. A few studies have looked at the use of nonsteroidal antiinflammatory drugs (NSAIDs), nifedipine, cromolyn, or nebulized bupivacaine for managing cough, but further studies are needed. Any aim 2 participants developing a cough (that is deemed new and significant by the study participant; and/or is grade 2 or higher as per DAIDS toxicity grading criteria; needs to involve the SOC and SSC. Each case will be handled on a one-on-one basis and decisions to hold or discontinue study medication will be made depending on the severity, progression (or lack thereof) and response to holding/discontinuing study medication. (NOTE: Please refer to "Table 3: Aim 2 Study Medication (Matched Placebo) Dose Titration Algorithm" for specific details).

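### As worded, the losartan substitution allows, without clearly intending, an active ARB for control participants; the text needs an arm-specific rule

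*Combined protocol and SAP*

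**What the plan says.** Section 5.0 (Aim 2, Study Medication) defines the control treatment: "Participants in the control arm will receive a matched placebo". That placebo is matched to lisinopril. No losartan placebo is described.

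Section 5.0 (Alternative medications) moves patients with side effects of lisinopril, cough above all, to losartan "at a dose of 25 or 50 mg/day (depending on the dose of lisinopril (or matched placebo) they were receiving". On unblinding it says: "Patients in need of anti-hypertensive treatment that developed a refractory cough while on study medication will all need to be unblinded". The main reason given is that the reaction be recorded so that ACE inhibitors are not prescribed again. The paragraph then refers to Figure 2, which is not visible in this copy.

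Section 6.0 (Risks of study medication) covers the same switch more broadly: "Any patients experiencing persistent/refractory cough that is deemed possibly related to their lisinopril therapy" "will be switched to an equivalent dose of the ARB losartan, as described above". Those who switch stay on study, "as a switch from an ACEi to an ARB is an allowable study substitution". Under Refractory Cough it adds committee involvement: "Each case will be handled on a one-on-one basis and decisions to hold or discontinue study medication will be made".

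For pregnancy, Section 5.0 states its rule by arm. The participant is unblinded, and the study drug, "if on active study medication; i.e. lisinopril) will be discontinued immediately". The angioneurotic edema paragraph of Section 6.0 has the same form.

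**The concern.** Section 4.0 blinds study physicians as well as participants. When a cough appears, a physician can judge that it may be due to lisinopril but cannot know whether the patient takes it. A rule that doses losartan by the lisinopril or placebo dose, with no step that separates the arms, can put a control on active drug.

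That control would be taking a RAAS inhibitor, the kind of treatment Aim 2 tests, and would still be analysed as a control under intention to treat. Section 4.0 gives minimising crossovers as one purpose of the placebo design, and Section 3.0 excludes current ACE inhibitor or ARB users at entry, but no readable sentence extends that bar to the study period. At stake are some dilution of the three uACR primary endpoints and losartan exposure in people whose cough lisinopril did not cause.

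**Working it through.** **Text side by side**

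| Point | Readable text |
|---|---|
| Who is switched | Section 5.0: patients with side effects attributed to lisinopril. Section 6.0: any refractory cough judged possibly related |
| Dose | Set by the lisinopril or placebo dose |
| Losartan placebo | None described |
| Unblinding at the cough switch | Section 5.0: only if blood-pressure treatment is needed; order relative to the switch not stated. Section 6.0: none stated |
| Action if found on placebo | None stated |
| Pregnancy, allergic reaction | Unblind, then act only if on active drug |

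The Figure 2 caption also says that patients removed after failing lisinopril or losartan are unblinded at that point. This suggests that some could reach losartan still blinded.

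**Inputs for the size (Section 8.0 and Table S1).** 140 randomised and 126 analysed per arm; alpha 0.017 two-sided (z = 2.387). Aim 2A: 12% vs 30%, or 16% vs 40% (HR 2.5). Aim 2B: 60% vs 25%. Aim 2C: difference 0.24 on the log scale, SD 0.58.

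**The plan's own figures first**
- 2A, 12%: events = 126 × (0.12 + 0.30) = 52.9; power = Φ(ln 2.5 × √52.9 / 2 − 2.387) = 0.828. Table 3 gives 0.828.
- 2A, 16%: 70.6 events, power 0.928. Table 3 gives 0.928.
- 2B: 107.1 events, power 0.984. Table 5 gives 0.984.
- 2C: power = Φ(0.24 / (0.58 × √(2/126)) − 2.387) = 0.815. The plan says approximately 80%.

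**With crossover.** Let p be the share of controls switched and e the losartan effect relative to lisinopril (1 = full, 0.5 = half).
- 2C difference = 0.24 × (1 − p × e).
- 2A control rate = 0.12 + 0.18 × p × e, or 0.16 + 0.24 × p × e. The HR and events are recomputed from it.
- 2B control rate = 0.60 − 0.35 × p × e.

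The range p = 1-5% is an assumption: 140 × 0.01 = 1.4 and 140 × 0.05 = 7 people.

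| Scenario | 2C | 2A, 12% | 2A, 16% | 2B |
|---|---|---|---|---|
| No switch | 81.5% | 82.8% | 92.8% | 98.4% |
| p = 1%, e = 1 | 80.6% | 81.6% | 92.0% | 98.2% |
| p = 5%, e = 1 | 76.8% | 76.3% | 88.4% | 97.4% |
| p = 5%, e = 0.5 | 79.3% | 79.7% | 90.8% | 98.0% |

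For example, at p = 5% and e = 1, the 2A (12%) control rate is 0.129, the HR is 0.30 / 0.129 = 2.326 and the events are 126 × 0.429 = 54.1.

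**Whole people needed to fall below 80% (p = people / 140)**
- 2C, full effect: 2 people leave 80.25%; 3 leave 79.6%. Half effect: 5 people.
- 2A (12%), full effect: 3 people leave 80.1%; 4 leave 79.2%. Half effect: 7 people.

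**The case against.** The strongest reply is that the whole point hangs on one parenthesis. The mention of matched placebo follows almost every dose in Sections 5.0 and 6.0 and may be habit. The operative wording concerns lisinopril: its side effects, a change from it, a move from an ACE inhibitor to an ARB. A placebo recipient has no ACE inhibitor to leave. The angioneurotic edema paragraph even lists the ARB as active study medication. Both specific cough-switch sentences in Section 5.0 carry the same blood-pressure condition as the unblinding sentence, so those switched under them are also those unblinded. Figure 2 may show the branch explicitly.

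Much of this stands. A reader might infer that the protocol has no arm-specific rule, or that it means to give controls losartan. Neither can be asserted: the wording leans toward the active arm, and a figure lost from this copy is not missing from the plan.

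The reply does not close the gap. Blinded physicians cannot apply wording that depends on knowing the arm. Section 6.0 has neither the blood-pressure condition nor an unblinding step. The committee sentence concerns holding or stopping study medication, not who may receive losartan. Section 8.0 also plans on-treatment and per-protocol analyses, but does not define them or say how a control on losartan would be classed.

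**Conclusion.** A minor point that holds for the readable text: an active ARB for controls is permitted but not clearly intended. Confidence is medium because Figure 2 could resolve it.

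A reader might infer that the primary comparison is compromised. It is not: intention to treat remains valid, and the expected effect is modest dilution toward the null. A reader might also apply the 5-15% cough frequency in Section 6.0 to controls. That is a frequency on ACE inhibitors, and the documents give none for placebo.

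The size rests on two assumptions: 1-5% of controls switch, and losartan 25-50 mg has between half and all of the lisinopril effect. Full effect is the upper bound. Passing below 80% should not be over-read: Section 8.0 claims only approximately 80% for 2C and for 2A at 12%, and calls its calculations likely conservative because they ignore baseline covariates and repeated uACR values.

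**What to change.** In the alternative-medications text of Section 5.0 and the cough text of Section 6.0, use the rule form already written for pregnancy and allergic reaction:
- Unblind before any switch to losartan.
- Give losartan only if the participant was on lisinopril.
- If on placebo, give no ACE inhibitor or ARB as study substitution, treat blood pressure with another class if needed, and keep all uACR visits.
- Check Figure 2 and make it agree.

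Sample size and drug supply do not change. The amendment needs review by both IRBs. A few more participants would be unblinded than Section 5.0 now requires, which could affect quality-of-life, Karnofsky and adverse-event relatedness ratings but hardly the laboratory uACR.

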6.0 Study Safety Monitoring Plan

Study participants will be recruited and consented at AKTH, Kano, Nigeria. Adherence to human subject regulations will primarily be the responsibility of the Multiple PIs. The study team will adhere to all requirements by: (i) developing a study protocol that is able to meet its stated research objectives, and thus reflect adequate risk-benefit ratios for human subjects; (ii) specifying study procedures in the protocol that protect the rights and safety of human subjects; (iii) developing a recruitment script and informed consent forms that include all elements of consent required by Federal regulations and accurately represents study requirements, risks, and benefits in language that is understandable to study participants, including human subject considerations; and (iv) monitoring adherence to protocol specifications and human subject requirements. The consent forms, protocol, and any subsequent modifications will be reviewed and approved by the Institutional Review Boards (IRB) at Vanderbilt University (FWA00005756), and AKTH (FWA00010841).

A. Adverse Event (AE) Assessment

1. Anticipated risks

Risks that are expected/anticipated as part of participation in the study are detailed in the study information and consent forms that will be distributed to and reviewed with patients by trained study team members. These risks are described below, along with steps that will be taken to minimize these risks:

Risks of blood draws: As described in Study Procedures (Section 6.0), blood specimens will be collected from each participant by routine venipuncture. The risks of venipuncture include discomfort at the site of puncture; possible bruising and swelling around the puncture site; and rarely an infection. We expect no additional psychological or social harms to occur. Other risks may include pain, bleeding, or bruising where the needle enters the skin; lightheadedness; and in rare cases, fainting or infection. These risks will be minimized by hiring study staff who are well trained in phlebotomy and other clinical procedures.

Risks of study medication (lisinopril and losartan)

The common side effects of lisinopril includes the following: cough, headache, dizziness, depressed mood, drowsiness, gastrointestinal symptoms such as nausea, upset stomach, vomiting or diarrhea, and skin symptoms such as mild itching or a rash. Any patients experiencing persistent/refractory cough that is deemed possibly related to their lisinopril therapy (as a refractory cough has been reported in as many as 6-8% of participants, with higher rates seen in person of African descent (up to 12% in some studies), will be switched to an equivalent dose of the ARB losartan, as described above. Patients switching from lisinopril to losartan will remain on study (Aim 2), as a switch from an ACEi to an ARB is an allowable study substitution. Common side effects of losartan include the following: cold or flu-like symptoms such as stuffy nose, sneezing, sore throat, fever; dry cough; muscle cramps; pain in legs or back; stomach pain or diarrhea; headache or dizziness; tired feeling or insomnia.

Refractory Cough: Cough occurs in 5-15% of patients. It is not dose- or brandrelated, is more frequent in women than men, and is more frequent in persons of African descent (blacks) than Caucasians (whites). It usually develops within 1 week to 6 months following ACEi initiation and typically resolves within 4 days of cessation. Study investigators need to be aware of a confounding congestive heart failure cough and remember that changing to another formulation sometimes helps. NOTE: Persons with a history of chronic h/o congestive heart failure are not eligible for aim 2. Cough is not a reason to discontinue treatment unless it persists (and or escalates in intensity/severity) and/or study participants feel that they cannot tolerate it. A few studies have looked at the use of nonsteroidal antiinflammatory drugs (NSAIDs), nifedipine, cromolyn, or nebulized bupivacaine for managing cough, but further studies are needed. Any aim 2 participants developing a cough (that is deemed new and significant by the study participant; and/or is grade 2 or higher as per DAIDS toxicity grading criteria; needs to involve the SOC and SSC. Each case will be handled on a one-on-one basis and decisions to hold or discontinue study medication will be made depending on the severity, progression (or lack thereof) and response to holding/discontinuing study medication. (NOTE: Please refer to "Table 3: Aim 2 Study Medication (Matched Placebo) Dose Titration Algorithm" for specific details).

Teratogenicity (Pregnancy Considerations): Lisinopril has been found to be teratogenic in mice and therefore is classified as class D by the FDA. All women of childbearing age (and potential) in this study will be extensively counseled about these potential risks and will be linked to family planning/spacing services, if desired. They will also undergo urine pregnancy testing at the beginning of the study and every three months at no cost. Any participant found to be pregnant will be withdrawn from the study. In addition, all women of childbearing age (and potential) will be extensively counseled and told to come immediately to clinic if they suspect for any reason that they may have become pregnant; i.e. missed/delayed menses, unexpected weight gain, etc.

Hyperkalemia: Given the potential risk for hyperkalemia in this study population, all study team members will be trained to educate participants on the risk of hyperkalemia, as well as prevention measures (e.g. maintaining adequate hydration, avoiding potentially nephrotoxic substances such as traditional medicines, etc.). Study team members will also train participants to recognize signs and symptoms of hyperkalemia, and study clinicians will be specifically trained on the risk, diagnosis, and management of hyperkalemia. We will explain to all study participants that lisinopril may cause hyperkalemia, and we will explain this in detail in the consent also strongly encouraging all study participants to notify our study staff before initiating any new medications or over-the-counter remedies, as we want to be sure that none of the new medications they are planning to start are associated with the possible risk of precipitating hyperkalemia. To protect study subjects and monitor them for this possible side effect, we will be performing frequent serum electrolyte monitoring; scheduled at least every three months while on study (Aim 2), including one additional serum electrolyte safety check visit at one week and at one month for all Aim 2 participants. (NOTE: Please refer to "Table 3: Aim 2 Study Medication (Matched Placebo) Dose Titration Algorithm" below for specific details). Participants will be extensively educated and told to call or come into the clinic if they experience decreased urine output, and/or fatique. palpitations. dyspnea. lightheadedness. generalized fatigue/malaise. Patients receiving concomitant medications that have also been known to potentially cause hyperkalemia (i.e. cotrimoxazole (Emtrim™), the ARV

medication dolutegravir (DTG), and other medications) will undergo more frequent serum electrolyte/safety monitoring.

Angioneurotic edema: Angioneurotic edema, which occurs in 0.1-0.2% of patients, usually develops within the first week of therapy but can occur at any time. This life-threatening adverse effect also occurs with angiotensin II receptor blockers but to a lesser extent. Any patient with a history of angioneurotic edema, whether related to an ACE inhibitor, angiotensin receptor blockers (ARBs), or another cause, should not be given an ACE inhibitor. (NOTE: any allergic reaction that is "definitely related" or "possibly related to study medication" that involves generalized urticaria OR angioedema with intervention indicated OR symptoms of mild bronchospasm is classified as a grade 3 acute allergic reaction and an SAE is needed and the participant is immediately unblinded, and if on active study medication (ACEi or ARB) it is to be discontinued immediately, and this allergic reaction is to be documented in their medical record. If the participant has acute anaphylaxis OR life-threatening bronchospasm OR laryngeal edema; this is a grade 4 acute allergic reaction and an SAE is needed and the participant is immediately unblinded, and if on active study medication (ACEi or ARB) it is to be discontinued immediately, and this allergic reaction is to be documented in their medical record.

Changes in blood pressure (Hypotension): Lastly, lisinopril may also cause and/or exacerbate changes in blood pressure, specifically hypotension given its primary indication for use as an anti-hypertensive agent. Such changes can occur at any time (and at any dosage) while on lisinopril, but in most cases reductions in blood pressure +/- with the associated symptoms of hypotension (i.e. dizziness, lightheadedness, fatigue/malaise, new onset or worsening headache, etc.) occur within the first 1-4 weeks following lisinopril (ACEi) initiation. To protect study subjects and monitor them for this possible side effect, we will be performing frequent blood pressure (BP) monitoring; scheduled at least every three months while on study (Aim 2), including one additional blood pressure (BP) safety check visits at one week and at one month for all Aim 2 participants. (NOTE: Please refer to "Table 3: Aim 2 Study Medication (Matched Placebo) Dose Titration Algorithm" below for specific details). Participants will be extensively educated and told to call or come into the clinic if they experience lightheadedness, dizziness, fatigue/malaise, weakness, new onset or worsening headache, etc. Patients receiving concomitant medications that have also been known to potentially cause or exacerbate changes in blood pressure (i.e. other antihypertensive medications such as thiazide diuretics (i.e. hydrochlorothiazide (HCTZ), etc.), calcium channel blockers (i.e. nifedipine, amlodipine, diltiazem, etc.), ß (Beta) blockers (i.e. metoprolol, propranolol, atenolol, carvedilol, etc.) and other classes of/specific anti-hypertensive (i.e. hydralazine, clonidine, etc.) and/or anti-anginal/cardiac protective medications (i.e. nitroglycerin, isosorbide monoand dinitrate, etc.) will undergo more frequent blood pressure/safety monitoring.

	Study Medication (Matched Placebo)			
Parameter /	Systolic blood pressure (SBP)	Serum potassium (K+)		
Guidelines to follow				
Step 1 to 2	SBP > 110 (ESCALATE)	K+ < 5.0 (ESCALATE)		
(5 mg/d ↑ to 10	SEF > THE (ESCALATE)	RISOLENCE)		
mg/d)	SBP 100-110 (Repeat BP and $\sqrt{100}$ for	K+ 5.0 – 5.5		
	symptoms/perform orthostatics) (Escalate	(Repeat BMP and have patient come back in		
	only if repeat SBP > 110 or repeat SBP	1-2 days for safety $$; if repeat K+ < 5.0 and		
	100-110 without symptoms and based on	creatinine stable—ESCALATE;		
	record review—confirmed that patient's	If repeat K+ 5.0 – 5.5; Hold and repeat BMP in		
